1.28.3 REPORTING UNANTICIPATED PROBLEMS TO PARTICIPANTS

N/A

STATISTICAL CONSIDERATIONS

1.29 STATISTICAL HYPOTHESES

- Primary Efficacy Endpoint(s):

To determine if treatment with topical beclomethasone applied on microsphere to the olfactory cleft results in improved olfactory function in long-COVID hyposmics, compared to placebo. Type of comparison: superiority. Time period: 6 weeks and 18 weeks post-enrollment.

Null hypothesis: There is no difference in SIT score with drug treatment or placebo.

Alternative hypothesis: Drug treatment results in improved SIT score.

- Secondary Efficacy Endpoint(s):

To assess olfactory-specific quality of life measure in treated versus placebo groups.
Type of comparison: superiority. Time period: 6 weeks and 18 weeks post-enrollment.

Null hypothesis: There is no difference in QOD score with drug treatment or placebo.

Alternative hypothesis: Drug treatment results in improved QOD score.

1.30 SAMPLE SIZE DETERMINATION

Number of participants to enroll to have adequate power to test the key hypotheses for the study:

Placebo group: 10

Treatment group: 10

- Target study sample size: 10 subjects in each arm, 20 subjects total. Anticipated number to be screened in order to reach the target enrollment: 50 subjects
- *Outcome measure used for calculations: SIT score*
- *Test statistic: t-test*
- *Null and alternative hypotheses:*
 - Null hypothesis: There is no difference in SIT score with drug treatment or placebo.
 - Alternative hypothesis: NAC treatment results in improved SIT score.
- *Type I error rate (alpha): 0.05*
- *Power level: 0.8*
- *Assumed mean and variance:*
 - Placebo group, μ_1 : SIT=24 \pm 4
 - Treatment group, μ_2 : SIT=29 \pm 4

Reference: "Hypothesis Testing: Two-Sample Inference - Estimation of Sample Size and Power for Comparing Two Means" in Rosner, Bernard Fundamentals of Biostatistics, Belmont, Calif. : Duxbury Press, [1995].

SIT score of 24 is used for the placebo group because this is a score categorized as severe hyposmia (reduced olfaction). Based on published reports and our experience with long-COVID hyposmia subjects, we anticipate identifying and enrolling patients with a mean score of approximately 24 and a variance of approximately 4.

In terms of estimated possible improvement in SIT score with drug treatment, we have chosen an increase of 5 ± 4 points, because a jump of more than a few points on a repeat SIT test after one month is considered to be greater than just random chance³; (and [name], *personal communication*). There are no published data available for specifically measuring olfactory change following treatment with beclomethasone applied to the olfactory cleft topically for post-viral hyposia.

- *Anticipated impact of dropout rates, withdrawal, missing data, etc. on study power:* to compensate for such issues, we have increased our sample size by 1 subject per group.
- *Secondary endpoint:* We have included a secondary endpoint to measure quality of life via a validated questionnaire (QOD). We have no specific guides for mean or variance for the questionnaire in terms of possible beclomethasone or placebo treatment, so no calculations are possible. Nonetheless, a simple questionnaire poses no cost or risk, such that we see no reason to not collect these data.

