1.32.1 DATA

Data (SIT scores, QOD scores) will be presented as means with standard deviations, as well as range. Placebo and drug-treated groups will be compared statistically, with $p < 0.05$ considered significant, via two-tailed t-test. If data are not normally distributed, nonparametric testing or appropriate post-hoc corrections will be applied.

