1.32.2 ANALYSIS OF THE PRIMARY EFFICACY ENDPOINT(S)

Primary endpoint is SIT score at 6 weeks and 18 weeks.

Placebo and drug-treated groups will be compared. SIT (mean \pm sd) will be compared via two-tailed t-test. SIT scores may range from 0-40, and normal scores are well-established. An assignment of normosmia, mild hyposmia, moderate hyposmia, severe hyposmia, anosmia, or probable malingering can be made based on SIT score.

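### Section 1.30 claims 80% power with a dropout allowance included, but on its own inputs the planned two-tailed t-test has about 75% power with 10 evaluable per arm

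*Combined protocol and SAP*

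**What the plan says.** Section 1.30 (Sample Size Determination) sets 10 subjects per arm, 20 in total. Its inputs are SIT 24 ± 4 on placebo and 29 ± 4 on treatment, "Type I error rate (alpha): 0.05", "Power level: 0.8" and "Test statistic: t-test". It does not say whether the test is one- or two-sided. For dropout, withdrawal and missing data it says that "to compensate for such issues, we have increased our sample size by 1 subject per group". It gives no sample size before that increase. In the explanatory text the expected patients are described as having "a mean score of approximately 24 and a variance of approximately 4".

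The analysis sections do fix the sidedness. In section 1.32.1 p < 0.05 is "considered significant, via two-tailed t-test", and in section 1.32.2 the SIT scores "will be compared via two-tailed t-test". The alternative hypothesis in section 1.29 is directional: "Drug treatment results in improved SIT score".

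Two other sections affect how many subjects are analysed. Section 1.23 says that treated subjects who later withdraw will be replaced, and that those who do not complete both applications are left out of the outcome analysis. Section 1.31 lists 10 per arm in the analysis dataset.

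**The concern.** If 10 per arm already includes one extra subject, the calculated requirement was 9. For a 5-point difference with SD 4, 9 per arm looks too few for 80% power in a two-tailed test, and 10 looks marginal. The word variance adds doubt: a variance of 4 is an SD of 2, which would give a very different sample size.

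The stated power is the benchmark for reading a non-significant result. If the true difference were the assumed 5 points, the plan implies a 20% chance of missing it. If the chance is really 25% to 30%, a null result would be given more weight than it deserves. A reader also cannot reproduce the calculation from the text as it stands.

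**Working it through.** **Inputs.** Difference 29 − 24 = 5; SD 4; alpha 0.05; target power 0.80; equal arms; t-test (all section 1.30). Two-tailed (sections 1.32.1 and 1.32.2). The ± is read as an SD because section 1.32.2 uses it that way for SIT. All figures are for one comparison at one time point.

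**Step 1. Reproduce the plan's figure.** The normal-approximation sample size per arm is n = 2 × SD² × (z_alpha + z_power)² / difference².

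- Two-sided: 2 × 16 × (1.960 + 0.842)² / 25 = 10.05, which rounds up to 11. Power at n = 10 is 79.8%, essentially the stated 0.8, but with nothing added for dropout.
- One-sided: 2 × 16 × (1.645 + 0.842)² / 25 = 7.91, so 8. Adding 1 gives 9, not 10.
- One-sided t-test: 76.8% at 8 and 81.4% at 9. The requirement is 9, and 9 + 1 = 10.

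Two routes therefore lead to 10: a two-sided normal approximation without the allowance, or a one-sided t-test with it. Neither fits both the allowance and the two-tailed t-test.

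**Step 2. Power of the planned test.** For the t-test, power comes from the noncentral t distribution with 2n − 2 degrees of freedom and noncentrality 5 / (4 × √(2/n)). At n = 10 the noncentrality is 2.795, with a two-sided critical value of 2.101 on 18 degrees of freedom. At n = 9 the values are 2.652 and 2.120 on 16.

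| Evaluable per arm | Two-sided t-test | Two-sided normal approximation | One-sided t-test |
|---|---|---|---|
| 9 | 70.2% | 75.5% | 81.4% |
| 10 | 75.3% | 79.8% | 85.2% |
| 11 | 79.6% | 83.4% | 88.2% |
| 12 | 83.3% | 86.5% | 90.7% |

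A simulation of the two-sided t-test with 400,000 trials per sample size gave 70.1% at 9 and 75.3% at 10. The planned test first passes 80% at 12 evaluable per arm.

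**Step 3. Difference detectable with 80% power.** For the two-sided t-test with SD 4 it is 5.3 points at 10 per arm and 5.6 points at 9 per arm.

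**Step 4. The variance wording.** A variance of 4 means SD 2. The two-sided normal formula then gives 2 × 4 × (1.960 + 0.842)² / 25 = 2.5 per arm. The t-test would have 83.6% power with 4 per arm and over 99% with 10. A sample of about 10 per arm is consistent only with SD 4.

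**The case against.** The strongest defence is that 10 per arm is not arbitrary. The two-sided normal approximation gives 79.8% at 10, which anyone would report as 80%, so the gap to 75% comes from using the t distribution rather than the normal. That stands as an explanation of the number. It does not rescue the text: section 1.30 names a t-test, and on the normal route all 10 subjects are needed before any allowance. At 9 per arm both two-sided methods fall short.

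The second defence is replacement. A reader might infer that 9 per arm, and so 70%, is what the plan will deliver. The documents do not support that as the default. Section 1.23 replaces treated subjects who withdraw, section 1.24 counts those lost to follow-up as withdrawn, and section 1.31 lists 10 per arm. The 70% applies only if one subject per arm is lost and not replaced. With full replacement the power is 75%, still below the claim.

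A reader might also conclude that the authors ran a one-sided calculation. The directional alternative makes that plausible, but the plan gives neither a base sample size nor a sidedness in section 1.30. An allowance that was described but never added is equally possible.

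The word variance is a slip: the ± notation shows what was meant, and no result changes. It still needs correcting, because the sentence describes the calculation's key input wrongly.

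Finally, it is tempting to argue that the placebo arm will also improve and that power is therefore much lower. Section 1.30 states both group means, so the 5-point between-arm difference is explicit, and the documents give no figure for placebo change. That is a debatable planning assumption, outside this arithmetic.

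**Conclusion.** The point holds. On the plan's own inputs, 80% power, an allowance of one subject per group and a two-tailed t-test with 10 per arm cannot all be true. The planned test has 75% power at 10 evaluable per arm and, if one subject per arm is lost without replacement, 70%. The shortfall is about 5 to 10 percentage points; equivalently, 80% power applies to 5.3 or 5.6 points rather than 5.

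This rests on SD 4 in both arms, a true difference of 5, equal arms and a single comparison at alpha 0.05. It does not depend on how the authors arrived at 10. The shortfall at 10 per arm is modest. The reason to act is that the stated figures contradict one another and the trial relies on them. The finding does not show that the design is unsound or that more patients are required.

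**What to change.** Keep 20 patients and correct section 1.30 in three places.

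1. Replace the power statement with: *Two-sided t-test, alpha 0.05, SD 4: 10 evaluable per arm give 75% power for a 5-point between-arm difference (70% if 9 per arm are evaluable); 80% power applies to a difference of 5.3 points (5.6 at 9 per arm).*
2. Where the ±4 is called a variance, write: *SD of approximately 4*.
3. Remove the claim that the sample size includes one extra subject per group.

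The cost is a text amendment and a slightly less favourable stated power; no patients are added and the analysis does not change. Keeping both the 80% and the allowance would instead take 12 + 1 = 13 per arm, 26 in total, or 6 more patients; the correction does not require this. The text should not promise that adjusting for baseline SIT will recover the missing power, because the documents give no correlation between baseline and follow-up scores.

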1.31 POPULATIONS FOR ANALYSES

- Intention-to-Treat (ITT) Analysis Dataset (i.e., all randomized participants):

Placebo group (n=10)

Beclomethasone treated group (n=10)

1.32 STATISTICAL ANALYSES

General Approach

1.32.1 DATA

Data (SIT scores, QOD scores) will be presented as means with standard deviations, as well as range. Placebo and drug-treated groups will be compared statistically, with $p < 0.05$ considered significant, via two-tailed t-test. If data are not normally distributed, nonparametric testing or appropriate post-hoc corrections will be applied.

1.32.2 ANALYSIS OF THE PRIMARY EFFICACY ENDPOINT(S)

Primary endpoint is SIT score at 6 weeks and 18 weeks.

Placebo and drug-treated groups will be compared. SIT (mean \pm sd) will be compared via two-tailed t-test. SIT scores may range from 0-40, and normal scores are well-established. An assignment of normosmia, mild hyposmia, moderate hyposmia, severe hyposmia, anosmia, or probable malingering can be made based on SIT score.

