1.7.3 ASSESSMENT OF POTENTIAL RISKS AND BENEFITS

Existing evidence is consistent with a very positive risk to benefit assessment. Prior clinical use of nasal steroids and the micro sponge report no adverse effects. The treatment involves only 2 applications of medication. There are no existing alternatives. Basic science studies provide evidence for promoting recovery using this drug or approach.

OBJECTIVES AND ENDPOINTS

OBJECTIVES	ENDPOINTS	JUSTIFICATION FOR ENDPOINTS
Primary		
To determine if topical intranasal treatment with beclomethasone on a micro sponge results in improved olfactory function, compared to placebo.	Olfactory function at 6 weeks and 18 weeks post-enrollment, as measured by Smell Identification Test (SIT).	SIT is a validated test for olfaction. Time points were chosen to test for early recovery of olfactory neurons versus evidence for successful regeneration, respectively.
Secondary		
To assess olfactory-specific quality of life measure in treated versus placebo groups.	Questionnaire on olfactory dysfunction (QOD) scores at 6 weeks and 18 weeks .	QOD is a validated tool for measuring quality of life related to olfactory loss.
Tertiary/Exploratory		
N/A		

STUDY DESIGN

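### SIT is primary at both week 6 and week 18, each tested at two-sided 0.05, with no rule for what counts as success, so the stated error rate or power fails depending on the reading

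*Combined protocol and SAP*

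**What the plan says.** The synopsis, the Objectives and Endpoints table, and sections 1.25, 1.29 and 1.32.2 all define the primary outcome as olfactory function at two visits. Section 1.32.2 puts it this way: "Primary endpoint is SIT score at 6 weeks and 18 weeks". The Objectives and Endpoints table gives the visits different purposes: "Time points were chosen to test for early recovery of olfactory neurons versus evidence for successful regeneration, respectively".

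The test and threshold are in section 1.32.1: "Placebo and drug-treated groups will be compared statistically, with $p < 0.05$ considered significant, via two-tailed t-test". That section also mentions corrections, but only for data that are not normally distributed, so it is not a rule for multiple tests.

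The sample size in section 1.30 rests on one t-test, with "Type I error rate (alpha): 0.05" and "Power level: 0.8". It does not say which visit this test belongs to. Section 1.33.2 lists the primary endpoint having been met among the reasons for which the study may be stopped, but no section defines what meeting it means.

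**The concern.** There are two primary tests, each at the full 0.05, and no statement of how they combine into one conclusion. The plan's own justification treats the visits as answering separate questions, so either could be presented as a positive finding. Nothing says whether that is intended or whether both must succeed.

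The two readings fail in different ways. Under an either-visit rule, the trial has two chances of a false positive and the 0.05 in section 1.30 is not held. Under a both-visits rule, error is controlled, but two hurdles must be cleared and power is below that of the single test used for sizing. With no rule fixed, the choice could be made after both results are known. In a trial of 20 participants, a chance result at one visit could then become the main finding.

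**Working it through.** **Inputs.** Two time points (1.32.2). Two-sided t-test at 0.05 for each (1.32.1). Mean SIT 24 against 29, SD 4, 10 per arm (1.30). The correlation ρ between a participant's week-6 and week-18 scores is not given, so it is an assumption and is varied.

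**Step 1: the plan's own figure.** The two-sided normal formula for one comparison gives n = 2 × [(1.960 + 0.842) × 4 / 5]² = 10.05 per arm. Power at 10 per arm is 79.8%, in line with the stated 0.8. The exact two-sided t-test has noncentrality 5 / (4 × √(2/10)) = 2.80 on 18 df, and power 75.3%. Both figures are for a single comparison. The gap from 0.80 to 0.75 is a separate point; 0.75 is the reference used below.

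**Step 2: either visit counts, no true effect.** With independent tests, the two-sided error is 1 − 0.95² = 9.75%. With correlation, it is 1 − P(|Z₁| < 1.96 and |Z₂| < 1.96) for a bivariate normal pair. Counting only false claims of benefit, it is 1 − P(Z₁ < 1.96 and Z₂ < 1.96), which is 1 − 0.975² = 4.94% under independence.

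| Assumed ρ | Error, either visit, two-sided | False claim of benefit (nominal 2.5%) |
|---|---|---|
| 0 | 9.75% | 4.94% |
| 0.3 | 9.5% | 4.8% |
| 0.5 | 9.1% | 4.5% |
| 0.7 | 8.4% | 4.2% |
| 0.8 | 7.8% | 3.9% |
| 0.9 | 7.0% | 3.5% |
| 0.95 | 6.5% | 3.2% |

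Simulated pairs of t-tests with 10 per arm (400,000 trials per correlation) agree within about 0.1 percentage point. By the normal calculation, the two-sided rate reaches 8% only when ρ is about 0.77 or lower.

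**Step 3: both visits required.** With no effect at either visit, the simulated chance that both tests are significant runs from about 0.3% (ρ = 0) to 3.5% (ρ = 0.95). It can never exceed 5%, because each test alone is held at 5%. Power for a true 5-point effect at both visits (5/4 = 1.25 SD), simulated with 10 per arm:

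| Assumed ρ | 0.3 | 0.5 | 0.6 | 0.7 | 0.8 |
|---|---|---|---|---|---|
| Power, both significant | 0.60 | 0.62 | 0.64 | 0.65 | 0.67 |

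The comparator is 0.75 for one test. Section 1.30 assigns the 5-point effect to no visit, so an equal effect at both is an assumption.

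**The case against.** A reader might infer that the chance of a false-positive primary result simply is 8 to 10%. The documents do not support that. It needs an either-visit success rule, which no section states, and a correlation of about 0.77 or lower, which no section gives. The same people take the same test 12 weeks apart, so a higher correlation cannot be excluded; at 0.95 the rate is 6.5%.

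It can also be said that the two-sided figure counts results favouring placebo, while the alternative in section 1.29 is improvement only. The chance of wrongly declaring benefit stays just under 5% even in the worst case. That is right, and it roughly halves the risk that matters most. But a two-sided 0.05 test allows 2.5% in that direction, so the inflation remains.

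Finally, this is a small single-site phase 2 trial with no planned interim analysis, and both visits can be reported whatever the rule. That limits the harm. It does not remove the need for a rule, because section 1.30 claims adequate power for the key hypotheses at a stated alpha.

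**Conclusion.** The concern holds as a missing decision rule. As written, the plan does not establish both its alpha of 0.05 and its power for the primary conclusion.

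- **Either visit suffices:** two-sided error is up to 9.75%, and still above 5% at a correlation of 0.95. The excess holds across the range examined; its exact size depends on the unstated correlation.
- **Both visits needed:** error is safe, and the loss is in power, about 0.08 to 0.15 below the single-test value of 0.75 (0.75 − 0.67 and 0.75 − 0.60). This assumes a 5-point effect at both visits and correlations of 0.3 to 0.8.

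The separate purposes given to the two visits lean towards the either-visit reading but do not establish it. A reader might also infer that week 18 is the more important visit. Nothing in the plan ranks it above week 6, and the sample-size rationale refers to a repeat test after one month, which is nearer to week 6.

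**What to change.** Before unblinding, state one rule in section 1.32.2 and say in section 1.30 which test or tests the sample size is meant to power. Section 1.19 keeps the randomization codes until the last participant has finished follow-up, so there should be time to do this.

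- **Simplest, a fixed sequence.** Test one sponsor-chosen time point first at two-sided 0.05 (for example week 18, which the plan links to regeneration). Test the other confirmatorily at 0.05 only if the first is significant; otherwise report it descriptively. This holds the familywise error at 5% whatever the correlation, and the threshold in section 1.32.1 can stay.
- **If the visits are to have equal standing, Hochberg over the two p-values.** Both are significant if the larger is at most 0.05; failing that, the smaller is significant if at most 0.025. State that this replaces the 0.05 threshold of section 1.32.1 for the primary endpoint.

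Neither option needs more data or participants. Under the fixed sequence, significance only at the second-ranked visit can no longer be claimed as a positive primary result. Hochberg lowers the chance of at least one significant visit: with a 5-point effect at both visits and 10 per arm, it is about 0.76 to 0.84 for correlations of 0.8 to 0.3, against 0.84 to 0.91 for unadjusted either-visit testing.

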1.32.3 ANALYSIS OF THE SECONDARY ENDPOINT(S)

Secondary endpoint is QOD score at 6 weeks and 18 weeks.

Placebo and drug-treated groups will be compared. QOD (mean \pm sd) will be compared via two-tailed t-test.

QOD scores may range from 0-75. There are 25 quality of life questions, scored 0-3 each. A lower score implies more severe dysfunction.

1.32.4 SAFETY ANALYSES

There is no formal safety endpoint being evaluated. AEs will be counted per event and will be presented as number of AEs and severity.

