1.23 PARTICIPANT DISCONTINUATION/WITHDRAWAL FROM THE STUDY

Participants are free to withdraw from participation in the study at any time upon request.

An investigator may discontinue or withdraw a participant from the study for the following reasons:

- If any clinical adverse event (AE), laboratory abnormality, or other medical condition or situation occurs such that continued participation in the study would not be in the best interest of the participant
- If the participant meets an exclusion criterion (either newly developed or not previously recognized) that precludes further study participation

The reason for participant discontinuation or withdrawal from the study will be recorded on the Case Report Form (CRF). Subjects who sign the informed consent form and are randomized but do not receive the study intervention may be replaced. Subjects who sign the informed consent form, and are randomized and receive the study intervention, and subsequently withdraw, or are withdrawn or discontinued from the study, will be replaced. Patients who do not complete the full course of study drug/placebo will be noted in the results tables, and they will not be included in the statistical analysis of outcome measures, since this is a simple comparison of SIT score between patients receiving 2 applications of drug versus placebo.

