1.27.4 TIME PERIOD AND FREQUENCY FOR EVENT ASSESSMENT AND FOLLOW-UP

The occurrence of an adverse event (AE) or serious adverse event (SAE) may come to the attention of study personnel during study visits and interviews of a study participant presenting for medical care, or upon review by a study monitor.

All AEs including local and systemic reactions not meeting the criteria for SAEs will be captured on the appropriate case report form (CRF). Information to be collected includes event description, time of onset, clinician’s assessment of severity, relationship to study product (assessed only by those with the training and authority to make a diagnosis), and time of resolution/stabilization of the event. All AEs

occurring while on study must be documented appropriately regardless of relationship. All AEs will be followed to adequate resolution.

Any medical condition that is present at the time that the participant is screened will be considered as baseline and not reported as an AE. However, if the study participant's condition deteriorates at any time during the study, it will be recorded as an AE.

Changes in the severity of an AE will be documented to allow an assessment of the duration of the event at each level of severity to be performed. AEs characterized as intermittent require documentation of onset and duration of each episode.

PI will record all reportable events with start dates occurring any time after informed consent is obtained until 7 (for non-serious AEs) or 30 days (for SAEs) after the last day of study participation. At each study visit, the investigator will inquire about the occurrence of AE/SAEs since the last visit. Events will be followed for outcome information until resolution or stabilization.

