1.32.8 TABULATION OF INDIVIDUAL PARTICIPANT DATA

A Table containing individual patient data will be included.

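### Section 1.32.4 makes the event the only counting unit for adverse events and plans no participants affected, no split by arm, no rule for recurrences and no safety denominator

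*Combined protocol and SAP*

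**What the plan says.** Section references follow the numbering in the body of the combined protocol and SAP, not its contents list.

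- **1.32.4 Safety Analyses** has two sentences. The first is "There is no formal safety endpoint being evaluated". The second is "AEs will be counted per event and will be presented as number of AEs and severity".
- **1.27.4** has adverse events recorded on the case report form with onset, severity, relationship and resolution, and those "occurring while on study must be documented appropriately regardless of relationship". It adds that "AEs characterized as intermittent require documentation of onset and duration of each episode".
- **1.30** gives the size: "Target study sample size: 10 subjects in each arm, 20 subjects total".
- **1.31** defines one analysis set, all randomised participants, with n=10 in each group. There is no safety set.
- **1.23** says that treated participants who "subsequently withdraw, or are withdrawn or discontinued from the study, will be replaced", and that those who do not complete the course are left out of the statistical analysis of outcome measures.
- **1.32.8** says only that "A Table containing individual patient data will be included". It does not say what the table holds.

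**The concern.** The rule in 1.32.4 fixes the event as the unit and stops there. Repeated events in one person are not independent, and in arms of 10 one individual can supply most of a total. What a reader of a phase 2 trial wants first is how many participants on drug, and how many on placebo, had a problem. An event total cannot answer that.

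Three details make the gap practical. The efficacy and baseline sections (1.32.2, 1.32.3, 1.32.5) each name the placebo and drug-treated groups; 1.32.4 does not. Section 1.7.1 lists localised nasal irritation as a possible risk of longer use, and irritation can come and go. And because treated participants who withdraw are replaced, those who stop because of an adverse event could drop out of view unless a denominator is defined.

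**Working it through.** **Inputs.** The documents give no adverse event rate and no numerical safety figure. The only number taken from them is 10 per arm (1.30), used as a denominator. The normal-approximation formula with the inputs of 1.30 gives 2 × [4 × (1.960 + 0.842)/5]² = 10.05 per arm, close to the stated 10. All event counts and rates below are assumptions.

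**Step 1: weight of one participant.** In participants affected, one person is 1/10 = 10 percentage points. In events, the same person can contribute any number.

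**Step 2: what totals can conceal.** Exact 95% limits are Clopper-Pearson: lower = Beta quantile(0.025; x, n−x+1), upper = Beta quantile(0.975; x+1, n−x), with n = 10.

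| Assumed pattern | Events, drug vs placebo | Participants, drug | Participants, placebo |
|---|---|---|---|
| One drug participant has 6 events, placebo none | 6 vs 0 | 1/10 (0.3% to 44.5%) | 0/10 (0% to 30.8%) |
| Seven drug participants have 1 event each, one placebo participant has 7 | 7 vs 7 | 7/10 (34.8% to 93.3%) | 1/10 (0.3% to 44.5%) |

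The first row shows a gap that comes from one person. The second shows no gap in events beside a gap of 60 percentage points in participants affected.

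**Step 3: recurrence.** Suppose the six events in the first row are six episodes of one intermittent complaint. Read as one adverse event with six documented episodes, the total is 1. Read as six adverse events, it is 6. Sections 1.27.4 and 1.32.4 together do not settle which.

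**Step 4: how often the two measures part company.** Assume identical arms of 10 and a mean of 0.5 events per participant. Clustering is modelled by a gamma-distributed individual rate (200,000 simulated trials per row).

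| Clustering | Event gap of 5 or more | Same, with participants affected differing by at most 1 | Share of large gaps |
|---|---|---|---|
| None | 15.1% | 0.8% | 0.8/15.1 = 5% |
| Moderate (shape 1) | 23.3% | 3.9% | 3.9/23.3 = 17% |
| Strong (shape 0.3) | 34.0% | 10.8% | 10.8/34.0 = 32% |

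So the event total misleads rarely when events do not cluster, and more often as they do.

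**Step 5: denominator.** Suppose one treated participant in an arm withdraws with an adverse event and is replaced. Eleven people in that arm then received product. Counting all treated gives 1/11 = 9.1%; counting only the 10 who remain gives 0/10. Section 1.32.4 does not say which applies.

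**The case against.** The strongest reply is that nothing is lost and little depends on the format. Every adverse event is recorded per participant, so incidence by arm can be derived at reporting. A listing of 20 people that included adverse events would make one person with many events visible. Serious events are reported individually and at once under 1.27.6, whatever the summary looks like. All of this stands, and it limits the weight of the point. It does not remove it: 1.32.8 does not say that its table shows adverse events or arm, and the one summary that is specified uses the weaker unit.

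A reader might infer four stronger things that the documents do not support.

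- *That incidence by arm will not or cannot be produced.* It is not planned; 1.32.4 does not rule it out.
- *That each episode is counted as a separate event.* Section 1.27.4 concerns documentation. Its wording fits one adverse event with several logged episodes at least as well.
- *That event counting inflates false positives.* With a mean of 1 event per person and negative-binomial dispersion 1, a naive test of counts gives p<0.05 in about 12% of null trials, against about 3% without clustering. But no such test is planned: the t-test rule in 1.32.1 covers smell and quality-of-life scores. At the same dispersion the figure falls to about 6% at a mean of 0.5 and about 1% at 0.2.
- *That chance differences are mainly due to event counting.* In the same mean-1 model, totals differ at least two-fold in 33% of null trials. The figure is 17% with no clustering, and about 20% for participants affected under the same clustering. At lower rates the two measures nearly agree: 47% versus 41% at a mean of 0.5, and 67% versus 65% at 0.2. Much of this is small-sample noise.

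Nor does the wide interval around 0/10 count against event totals. Zero events means zero participants affected, so the two measures carry the same information there.

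**Conclusion.** The point holds as a weakness in the descriptive safety summary. Section 1.32.4 sets the event as the sole unit and leaves out participants affected, arm, recurrence and denominator; no other section supplies them. In arms of about 10, the planned output can show a difference that comes from one person, or hide a difference as large as 7/10 versus 1/10. These are possibilities under assumed counts. How likely they are depends on event rate and clustering, on which the documents give nothing. No efficacy conclusion is affected. The change is worth making because this is the only safety summary planned in the statistical section and the better one costs almost nothing.

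**What to change.** Replace the second sentence of 1.32.4 with:

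> By arm, report the number and percentage of participants with at least one AE, at least one related AE and at least one SAE, each participant counted once at maximum severity, with exact 95% confidence intervals. The denominator is everyone who received at least one application, including those later withdrawn or replaced. Event counts are given as a supplementary column.

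Add one sentence saying whether repeat episodes of an intermittent event count once or separately in that column. It would also help to state in 1.32.8 that the individual table shows arm and adverse events.

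The cost is a few sentences and a slightly larger table. Onset, severity and relationship are already to be recorded for each participant, so no new data are needed.
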